***Exploratory endpoints:***

- Specific markers of inflammation, lipids, glucids, fibrosis, bone remodeling change from baseline to end of treatment (week 24).
- Transient Elastography (TE) and Controlled Attenuation Parameter (CAP) change from baseline to end of treatment (week 24)
- If deemed necessary: Immunohistochemistry: change in the semiquantitative score of ballooning and stellate cell activation from baseline to end of treatment (week 24).

The Hochberg procedure will be applied to take into account multiplicity of testing (no adjustment for safety parameters). Adjustment for multiplicity will be done for the two treatment group comparisons (high dose vs placebo and low dose vs placebo) but not for the number of studied parameters.

**Pharmacokinetic variables:** Trough plasma levels of lanifibranor will be assessed at V1 (week 4) and V3 (week 24).

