- Main plasma lipids levels (TC, HDL-C, calculated LDL-C, TG and apoA1) change from baseline to end of treatment (week 24) will be compared using GLM with the diabetes and dose as covariates. A mixed model for repeated measures will also be used to compare the time course of the response of each treatment group.
- Adiponectin change from baseline to end of treatment (week 24). Comparison tests and estimates of the difference in the change from baseline will be performed using GLM with the diabetes and dose as covariates. A mixed model for repeated measures will also be used to compare the time course of the response of each treatment group.
- Immunohistochemistry if deemed necessary: change in the semi-quantitative score of ballooning and stellate cell activation from baseline to end of treatment (week 24) will be compared using a Van Elteren rank test stratified on diabetes.

The SAP will provide more details on the presented analyses as well as on other exploratory criteria such as quality of life assessment.

All secondary efficacy analyses will be performed using a mixed model for repeated measures or an ANCOVA model if only one post-randomization measure is available. CMH test stratified on diabetes will be used for qualitative variables.

Exploratory analyses on the biomarkers measurements and other evaluations will be proposed and described in the statistical analysis plan.

The final version of the Statistical Analysis Plan will be issued before freezing of the database the break of the randomization code. Any clarification brought in the SAP concerning handling of data and statistical analyses will prevail over any other interpretations of the protocol unless it is the source of major inconsistencies.

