#### *4.1.5 Treatment groups comparison*

For statistical tests, the type I error risk of these will be set at 5% (2-sided) without adjustments for multiplicity testing, unless specified otherwise.

P-values will be presented with 3 decimals. Any p-value less than 0.001 will be presented as <0.001, even if it would normally round up to 0.001.

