#### **Hochberg procedure for multiplicity testing**

When specified, the ascending Hochberg procedure will be used to adjust for multiplicity testing. This procedure is a powerful tool that decreases the false discovery rate: this is the expected proportion of "discoveries" (significant results) that are actually false positives. Adjusting the rate helps to control for the fact that sometimes small p-values (less than 5%) happen by chance, which could lead to incorrectly reject the true null hypotheses. In other

words, the procedure helps to avoid type I errors (false positives). To run the procedure, the following steps will be followed:

1. Put the individual p-values (without multiplicity adjustment) in ascending order, from smallest to largest.
2. Assign ranks to the p-values. For example, the smallest has a rank of 1, the second smallest has a rank of 2.
3. Calculate each individual p-value's critical value, using the formula  $(i/m)Q$ , where:
  - $i$  = the individual p-value's rank,
  - $m$  = total number of tests,
  - $Q$  = the false discovery rate (type I error)
4. Compare original p-values to the critical ones from Step 3; find the largest p value that is smaller than the critical value.

As an example, the following table shows the result of 2 tests (*lanifibranor 800 mg vs. placebo* and *lanifibranor 1200 mg vs. placebo*) with their p-values. The list of p-values are ordered (Step 1) and then ranked (Step 2) in the 3rd column. The last column shows the calculation of the critical value with a false discovery rate of 5% (Step 3). For instance, last column for test 2 (*lanifibranor 800 mg vs. placebo*) is calculated as  $(2/2) * 0.05 = 0.050$ :

Test	p-value observed	Rank (i)	$(i/m)Q=(i/2)x0.05$
Lanifibranor 1200 mg vs. placebo	0.020	1	0.025
Lanifibranor 800 mg vs. placebo	0.028	2	0.050

As the p-value associated to the test "*lanifibranor 1200 mg vs. placebo*" (p-value = 0.020) is smaller than its associated critical value (critical-value = 0.025), the test is considered as statistically significant after multiplicity adjustment according to the ascending Hochberg procedure. Similarly, the test "*lanifibranor 800 mg vs. placebo*" is considered as statistically significant after multiplicity adjustment according to the ascending Hochberg procedure: p-value = 0.028 < critical-value = 0.050.

Comparison of treatment groups for **quantitative variables** will be performed using:

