#### 4.6.4 *Efficacy analysis*

The analysis of dose response relationship has been added in the SAP for primary criterion (see section 5.2.2.4) as well as an analysis which explores the evaluation of treatment effect after adjustment on the relative change in weight from baseline (see section 5.2.2.4).

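### SAP 4.1.5 names the Hochberg procedure but prints Benjamini-Hochberg cutoffs, and its rejection rule has no ending

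*SAP*

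**What the plan says.** Protocol 9.7.4 uses the ascending Hochberg procedure to hold the type I error of the primary tests at 0.05 two-sided overall. The synopsis limits its scope: "Adjustment for multiplicity will be done for the two treatment group comparisons", and not for the number of parameters studied.

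SAP 4.1.5 sets a default of 5% tests "without adjustments for multiplicity testing, unless specified otherwise" and then explains the Hochberg procedure. It says of it: "This procedure is a powerful tool that decreases the false discovery rate". It gives the critical value for rank i as (i/m)Q and defines Q as "the false discovery rate (type I error", so the two error rates are treated as one. The final step tells the reader to compare p-values with critical values and "find the largest p value that is smaller than the critical value". Nothing follows about which hypotheses are then rejected. The worked example (p = 0.020 and 0.028, cutoffs 0.025 and 0.050) judges each p-value against its own cutoff, ending with "p-value = 0.028 < critical-value = 0.050".

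SAP 5.2.2.1 sends the primary analysis to this section. SAP 4.1.5 also applies the procedure to the time course, straight after listing six pairwise contrasts among weeks 4, 14, 24 and 28 for each dose. SAP 5.2.3.8 instead applies it time point by time point. Neither place states m.

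SAP 4.6 lists the departures from the protocol's statistical section. Its entry on the efficacy analysis begins "The analysis of dose response relationship has been added in the SAP for primary criterion" and goes on to a weight-adjusted analysis. No change of multiplicity method is declared.

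**The concern.** There are three faults in the text.

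1. **Name and formula disagree.** Hochberg's step-up procedure is a familywise method. The (i/m)Q rule controls the expected share of false rejections among all rejections, which is a weaker guarantee. Because SAP 4.6 declares no such change, this reads as a mislabelled formula and not as a choice.
2. **The rule is unfinished.** A step-up rule must end by rejecting the hypothesis found and every hypothesis with a smaller p-value. The example does not supply this, because its p-values give the same verdict whether one steps up or compares one by one.
3. **The time-course family is not fixed.** The two formulas agree at m=2 and differ for every m of 3 or more, so an unstated m decides whether fault 1 has any effect.

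Protocol 9.7.4 adds weight to the SAP wording: "Any clarification brought in the SAP concerning handling of data and statistical analyses will prevail over any other interpretations of the protocol", with an exception for major inconsistencies. A programmer will work from the SAP text, so that text should be right as printed.

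**Working it through.** **Inputs.** Q = 0.05 and the cutoff (i/m)Q (SAP 4.1.5); m=2 for the dose-placebo tests (protocol synopsis, SAP 5.2.2.1); six contrasts per dose for the time course (SAP 4.1.5); 247 randomised (SAP 3.5), so about 247/3 = 82 per arm.

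**Step 1: reproduce the SAP's figures, m=2.**
- Printed formula: (1/2)(0.05) = 0.025 and (2/2)(0.05) = 0.050.
- Hochberg, 0.05/(m-i+1): 0.05/2 = 0.025 and 0.05/1 = 0.050.

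The SAP's cutoffs are reproduced and the two formulas agree.

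**Step 2: the missing ending, m=2.** Take p = 0.030 and 0.040. Stepping up, 0.040 is below 0.050, so both hypotheses are rejected. Comparing one by one as in the example, 0.040 passes (below 0.050) and 0.030 fails (above 0.025). The readings part only when both p-values lie in [0.025, 0.05). Simulated frequency (CMH test, two strata, shared placebo arm, 400,000 replicates per cell, n = 75 and 82 per arm, diabetic share assumed 30-50%):

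| Response rates | Both p-values in the window |
|---|---|
| Null | 0.2% |
| 10% placebo, 30% both doses | 0.6-0.8% |
| 10% / 20% / 30% | 0.5-0.6% |
| 15% placebo, 35% both doses | 0.9-1.2% |
| 10% placebo, 25% both doses | 1.4-1.7% |

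Under either reading, familywise error is 4.2-4.4%, and at-least-one-dose power at 10% vs 30% is 93% (n=75) or 95% (n=82).

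**Step 3: cutoffs if m=6.**

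| Rank | (i/6)(0.05) | 0.05/(7-i) | Ratio |
|---|---|---|---|
| 1 | 0.0083 | 0.0083 | 1.00 |
| 2 | 0.0167 | 0.0100 | 1.67 |
| 3 | 0.0250 | 0.0125 | 2.00 |
| 4 | 0.0333 | 0.0167 | 2.00 |
| 5 | 0.0417 | 0.0250 | 1.67 |
| 6 | 0.0500 | 0.0500 | 1.00 |

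For p = 0.008, 0.015, 0.022, 0.030, 0.040 and 0.200, the printed formula rejects five and Hochberg rejects one.

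**Step 4: familywise error if m=6.** Simulation of within-arm visit contrasts with covariance pooled over three arms, complete data, 60,000 replicates per cell (Monte Carlo error about 0.09 points at 5%). Correlations of 0.3, 0.6 and 0.8 and all effects are assumed. n=82:

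| Pattern | Printed formula | Hochberg |
|---|---|---|
| No visit differs | 4.0-4.6% | 3.6-4.2% |
| Week 28 differs by 0.2 SD | 4.3-6.8% | 2.6-3.5% |
| Week 28 differs by 0.3 SD | 5.6-8.3% | 2.9-4.3% |
| Week 28 differs by 0.5-1.0 SD | 7.4-8.8% | 3.7-4.6% |
| Weeks 4/14 vs 24/28 differ by 0.3 SD | 4.9-7.8% | 2.5-4.4% |
| Weeks 4/14 vs 24/28 differ by 0.5-1.0 SD | 7.4-8.4% | 3.9-5.1% |

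With an assumed 20% loss (n=66), the printed formula gives 5.2-7.9% for week 28 at 0.3 SD and 7.2-8.6% at 0.5-1.0 SD. A separate calculation with very large effects gave 8.4% against 4.4% when only week 28 differs. The false discovery rate stayed at or below 5% in every pattern of that calculation, so the printed rule does control FDR.

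**Step 5: how many contrasts.** SAP 5.2.3.8 to 5.2.3.10 ask for the time course of nine markers: fasting glucose, HbA1c, ALT, AST, GGT, total cholesterol, HDL-C, LDL-C and triglycerides. 9 x 6 x 2 doses = 108 contrasts. If each treatment group is taken to include placebo, 9 x 6 x 3 = 162.

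**The case against.** The best defence is that no promised guarantee fails. The protocol confines adjustment to the two dose-placebo comparisons, where the cutoffs are right. Adjusting the time course is an addition of the SAP, so a familywise rate of 7% or 8% is measured against a target nobody set for it. The SAP also shows its formula and speaks of false discovery openly. All of this stands, and it is why the point is minor. It does not make the label correct.

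Searching for the largest qualifying p-value only makes sense in a step-up rule, and the rival reading is incoherent because it passes the larger p-value and fails the smaller. That favours step-up, but the rule still has to be completed by whoever programs it.

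The m=6 consequence is conditional. The instruction in SAP 5.2.3.8 can be read as two doses at each visit, so m=2, and then nothing changes. The simulated rates also depend on the pattern. With weeks 4/14 and 24/28 differing by 0.2 SD, the printed formula gives only 3.8-6.2% at n=82, and if every visit differs no false rejection is possible.

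Finally, the glucose, lipid and liver-enzyme endpoints are all listed as secondary in the protocol synopsis and 9.1, but as change from baseline to week 24. Visit-to-visit contrasts within an arm are not that endpoint for any of them. The protocol's exception for major inconsistencies also limits how far the SAP text could override its named method.

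**Conclusion.** The concern holds and is minor. SAP 4.1.5 prints the Benjamini-Hochberg formula under Hochberg's name and omits the closing rejection statement; both follow from the text without assumptions. The primary cutoffs, the 5% error and the at-least-one-dose answer do not change. The only exposure for the primary analysis is a misread per-dose verdict in at most 1.7% of trials in the scenarios tried.

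For the time course, the mislabelling matters only if m is 3 or more. With six contrasts per dose, which is the plain reading of SAP 4.1.5, 108 within-arm laboratory contrasts would be reported as Hochberg-adjusted when they are FDR-adjusted. That size rests on m=6, two arms, and the assumed correlations and effects.

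**What to change.** In SAP 4.1.5, replace the last two steps by: order p(1) ≤ ... ≤ p(m); find the largest i with p(i) ≤ 0.05/(m-i+1); reject H(1) to H(i). Add p = 0.030 and 0.040, both rejected, as a worked example, since it separates the two readings. Remove the false-discovery wording from the description of Hochberg. State m for the time-course family, say whether placebo is included, and reconcile SAP 4.1.5 with SAP 5.2.3.8.

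If FDR control is what is wanted for the visit contrasts, name Benjamini-Hochberg for them and keep Hochberg for the dose-placebo tests.

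The cost is a few sentences and a line of code, with none for the primary test and none if FDR is named openly. If Hochberg is used for six contrasts, average power per true contrast falls by up to about 9 points in the scenarios tried: 72.2% to 63.5% at n=82 (weeks 4/14 vs 24/28 differing by 0.2 SD, correlation 0.8), and 66.6% to 57.5% at n=66 (0.3 SD, correlation 0.6). At 1.0 SD nothing is lost.

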The generalizability of the treatment effect across geographical area will be tested and the statistical strategy will be defined in the SAP once the sample size will be known by stratum and country and before the break of the randomization code.

There is no planned interim analysis for success. However, the DSMB may decide to perform some futility analyses in particular in case of safety concerns.

A series of sensitivity analyses will be performed to assess the robustness of results such as the use of a stratified test (country as a stratification factor), the use of other sets of patients (PP set, Evaluable set, Randomized set, completer set). In case of missing assessment at W24, the patient will be considered a non-responder. A responder is consequently a confirmed responder.

Secondary efficacy analyses:

- NASH improver rates in each dose will be compared to placebo using the Cochran Mantel Haenszel test stratified on diabetes.
- Percent of patients with resolution of NASH in each dose will be compared to placebo using the Cochran Mantel Haenszel test stratified on diabetes.
- Percent of patients with a change in components of SAF score in each dose will be compared to placebo using the Cochran Mantel Haenszel test stratified on diabetes.
- Percent of patients with at least 1-point improvement of fibrosis without worsening of NASH in each dose will be compared to placebo using the Cochran Mantel Haenszel test stratified on diabetes.

Planned exploratory analyses:

- Inflammatory markers (fibrinogen, hs-CRP, alpha2 macroglobulin and haptoglobin levels) change from baseline to end of treatment (week 24) will be compared using GLM with the diabetes and dose as covariates. A mixed model for repeated measures will also be used to compare the time course of the response of each treatment group.
- Transient Elastography and Controlled Attenuation Parameter change from baseline to end of treatment (week 24) will only be described.
- Glucose metabolism (fasting glucose and insulin, HOMA index and, in subjects with T2DM, HbA1c) change from baseline to end of treatment (week 24) will be compared using GLM with the diabetes

and dose as covariates. A mixed model for repeated measures will also be used to compare the time course of the response of each treatment group.

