- an Analysis of Covariance (**ANCOVA**) using the SAS MIXED procedure with the treatment and the diabetic status as covariates when specified

Or

- a Mixed Model for Repeated Measures (**MMRM**) when specified using the SAS MIXED procedure with:
  - a. The absolute change from baseline of the analysis variable as endpoint (MODEL statement of the MIXED procedure)
  - b. The time, treatment, the diabetic status, the interaction (treatment \* time) and the baseline value as fixed effects (MODEL statement of the MIXED procedure). Time, treatment and diabetic status being considered as categorical variables
  - c. A time repeated measure (REPEATED statement of the MIXED procedure) within each subject (SUBJECT = subject as option of the REPEATED

statement). An unstructured (type=UN) variance covariance matrix being used as option of the REPEATED statement

- d. The Kenward-Roger approximation to estimate denominator degrees of freedom and adjust standard errors (ddfm=kr option in MODEL statement)

In order to explore the validity of the model (and more accurately the assumption regarding independence, normality and constant variance of residuals), the following graphs will be provided: Q-Q plot of the residuals, distribution of residuals with its corresponding normal density estimate and scatterplot of residuals vs. predicted values.

With such models (ANCOVA, MMRM) different treatment effects will be evaluated:

- **Evaluation of treatment effect (Each dose vs. placebo) at week 24:** In order to evaluate each treatment dose versus placebo at week 24 the following contrasts of interest will be used:
  - o 800 mg/day vs. placebo: -1 for Placebo, 1 for 800 mg/day and 0 for 1200 mg/day
  - o 1200 mg/day vs. placebo: -1 for Placebo, 0 for 800 mg/day and 1 for 1200 mg/day.

In order to take into account multiplicity of tests, the ascending Hochberg procedure will be applied (see section 4.1.5).

- **Evaluation of dose effect (800 mg vs. 1200 mg) at week 24:** In order to evaluate the dose of 800 mg/day versus the dose of 1200 mg/day at week 24 the following contrast of interest will be used:
  - o 800 mg/day vs. 1200 mg/day: 0 for Placebo, -1 for 800 mg/day and 1 for 1200 mg/day
- **Time course of the response of each treatment group:** In order to evaluate the time course of the response of each dose (separately) at each time-point the following contrasts of interest will be used for each dose:

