Objectives/Endpoints	Type of analysis	Method of analysis	Population and imputation method
Glucose metabolism (fasting glucose, insulin, HOMA index, C-peptid, HbA1c and fructosamide)	Main analysis	Descriptive Treatment effect: MMRM or ANCOVA Time course: MMRM when possible	FAS – Observed Cases under treatment (considering only fasting values, when specified)
	Subgroups analysis (diabetic status) (HbA1c at for HbA1c)	Descriptive	FAS – Observed Cases under treatment (considering only fasting values, when specified)
Liver enzymes (ALT, AST, GGT, Alkaline Phosphatase, Total Bilirubin)	Main analysis	Descriptive Treatment effect: MMRM Time course: MMRM	FAS – Observed Cases under treatment
	Subgroup analysis (diabetic status)	Descriptive	FAS – Observed Cases under treatment
Plasma lipids levels (TC, HDL-C, LDL-C, TG, apoA1, FFA, Adiponectin, Leptin, APO B, APO C3 and FGF21)	Main analysis	Descriptive Treatment effect: MMRM or ANCOVA when specified Time course: MMRM when possible	FAS – Observed Cases under treatment considering only fasting values
	Subgroup analysis ; - diabetic status - statins at Baseline	Descriptive	FAS – Observed Cases under treatment considering only fasting values
Efficacy inflammatory markers (fibrinogen, hs- CRP, alpha2 macroglobulin, haptoglobin, IL-13, IL-17a, , IL-6, IL-1b, TNF-a, INFg)	Main analysis	Descriptive Treatment effect: ANCOVA when specified	FAS – Observed Cases under treatment

Objectives/Endpoints	Type of analysis	Method of analysis	Population and imputation method
Efficacy fibrosis markers (TIMP-1, TIMP-2, Hyaluronic acid, P3NP, NFS, FIB-4 score, ELF score, MACK-3, FIBC3, ABC3D, Cytokeratin M30, Cytokeratin M65, Liver iron content, MMP2, MMP9, Pro-C3)	Main analysis	Descriptive Treatment effect: ANCOVA when specified	FAS – Observed Cases under treatment
	Exploratory analysis	Cross-tabulation with the CRN-F score (F0-F1, F2-F3) when specified	FAS – Observed Cases under treatment
Efficacy chemistry markers (Plasma Iron, Transferrin, Ferritin)	Main analysis	Descriptive	FAS – Observed Cases under treatment

Subgroups of interest are :

(1)

- Biopsy length ( $\leq 8$ ,  $>8$  mm)
- SAF-A at Baseline (A2-A3, A4)
- CRN-F at Baseline (F0-F1, F2-F3)
- NAS score at baseline ( $<6$ ,  $\geq 6$ )
- BMI at Baseline (Obese, Non-Obese)Metabolic syndrome at Baseline (Yes, No)
- Insulin-resistance status at Baseline (Yes, No)
- Sex (Male, Female)

(2)

- NAS score at baseline ( $<6$ ,  $\geq 6$ )

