#### - Descriptive analysis

Fasting glucose and HbA1c assessed at Screening, Baseline, Week 4, Week 14, Week 24 and Week 28, as well as insulin, C-peptid, fructosamide and HOMA index assessed at Week 0 and Week 24, will be described over time using descriptive statistics by treatment group and diabetic status, in terms of:

- Raw values
- Absolute change from baseline

The 95% CI of the mean will also be provided.

- Status over time (Normal-Normal, Normal-Abnormal, Abnormal-Normal, Abnormal-Abnormal)

The 2 timepoints prior to first intake will have to be analysed: screening and baseline.

One graph will also be provided describing the raw values (with 95% CI) by treatment group over time (including screening values)

The HOMA index will also be described qualitatively over time using descriptive statistics by treatment group and diabetic status (HOMA < 3, ≥ 3).

- Absolute changes in HbA1c value will be described qualitatively over time using descriptive statistics by treatment group and diabetic status:
  - o Decrease of HbA1c (Decrease of 1%, No change (Change within ]-1% ; 1%[]), Increase ≥ 1%).
  - o Decrease of HbA1c (Decrease ≥ 0.5%, No change (Change within ]-0.5% ; 0.5%[]), Increase ≥ 0.5%)
- Evaluation of treatment effect (each dose versus placebo)

For fasting glucose, HbA1c, insulin and HOMA index, in order to evaluate each treatment dose versus placebo at week 24, a MMRM will be performed as detailed in section 4.1.5.

In order to take into account multiplicity of tests, the ascending Hochberg procedure will be applied (see section 4.1.5 for details).

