## 5.2.3.10 Plasma lipids levels

The following table describes for each parameter the collection time and the type of analyses to be done.

Parameter	Collection time	Main analyses (see section 5.2.3.8 describing the methodology)	Sensitivity analyses	Subgroup analyses
Total Cholesterol	Screening, Baseline, weeks 4, 14, 24 and 28	Descriptive analysis Treatment effect ( each dose versus placebo ) Time course of the response of each treatment group	None	By diabetic status (Yes, No) By Statins at baseline (Yes, No)
HDL-C	Screening, Baseline, weeks 4, 14, 24 and 28	Descriptive analysis Treatment effect ( each dose versus placebo ) Time course of the response of each treatment group	None	By diabetic status (Yes, No) By Statins at baseline (Yes, No)
LDL-C	Screening, Baseline, weeks 4, 14, 24 and 28	Descriptive analysis Treatment effect ( each dose versus placebo ) Time course of the response of each treatment group	None	By diabetic status (Yes, No) By Statins at baseline (Yes, No)
Triglycerides	Screening, Baseline, weeks 4, 14, 24 and 28	Descriptive analysis Treatment effect ( each dose versus placebo ) Time course of the response of each treatment group	None	By diabetic status (Yes, No) By Statins at baseline (Yes, No)
Apo A1	Baseline, week 24	Descriptive analysis Treatment effect ( each dose versus placebo )	None	By diabetic status (Yes, No) By Statins at baseline (Yes, No)
FFA	Baseline, week 24	Descriptive analysis	None	By diabetic status (Yes, No) By Statins at baseline (Yes, No)
Adiponectin	Baseline, week 24	Descriptive analysis Treatment effect ( each dose versus placebo )	None	By diabetic status (Yes, No) By Statins at baseline (Yes, No)
Leptin	Baseline, week 24	Descriptive analysis	None	By diabetic status (Yes, No) By Statins at baseline (Yes, No)
APO B	Baseline, week 24	Descriptive analysis	None	By diabetic status (Yes, No) By Statins at baseline (Yes, No)

Parameter	Collection time	Main analyses (see section 5.2.3.8 describing the methodology)	Sensitivity analyses	Subgroup analyses
APO C3	Baseline, week 24	Descriptive analysis	None	By diabetic status (Yes, No) By Statins at baseline (Yes, No)
FGF21	Baseline, week 24	Descriptive analysis	None	By diabetic status (Yes, No) By Statins at baseline (Yes, No)

Only fasting results will be considered for analyses.

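### The SAP leaves open whether markers measured once after baseline are adjusted for their baseline value

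*SAP*

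**What the plan says.** SAP 4.1.5 offers two models for quantitative variables.

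- **ANCOVA:** fitted "using the SAS MIXED procedure with the treatment and the diabetic status as covariates when specified". No baseline term is listed and the outcome is not stated.
- **MMRM:** fitted to absolute change from baseline, with time, treatment, diabetic status, treatment by time "and the baseline value as fixed effects".

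The later sections assign these models differently.

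- **SAP 5.2.1 (summary table):** "Treatment effect: ANCOVA", with the rider that this applies when specified, for inflammatory and fibrosis markers; "Treatment effect: MMRM or ANCOVA" for glucose parameters and plasma lipids. Covariates are not given.
- **SAP 5.2.3.8 (glucose metabolism):** for fasting glucose, HbA1c, insulin and HOMA, "in order to evaluate each treatment dose versus placebo at week 24, a MMRM will be performed as detailed in section 4.1.5". Two of these four have only one post-baseline value, since the same section describes glucose and HbA1c at several visits "as well as insulin, C-peptid, fructosamide and HOMA index assessed at Week 0 and Week 24".
- **SAP 5.2.3.10, 5.2.3.11 and 5.2.3.12 (lipids, inflammatory markers, fibrosis markers):** the analysis column of each table says "see section 5.2.3.8 describing the methodology".
- **Protocol 9.7.4:** change from baseline to week 24 in inflammatory markers, glucose parameters, lipids and adiponectin "will be compared using GLM with the diabetes and dose as covariates". The same section later calls for ANCOVA where only one post-randomization measure exists, again without listing covariates.

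No section from SAP 5.2.3.8 to 5.2.3.13 specifies an ANCOVA for any parameter.

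**The concern.** Two readings of the SAP are open for the same endpoint. Following 5.2.1 back to 4.1.5 gives a model without the baseline value. Following the marker tables to 5.2.3.8 gives the MMRM, which with one post-baseline visit is a baseline-adjusted ANCOVA. The estimates and p-values differ, and nothing in the text visible to us fixes the choice before the code is broken.

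If the ANCOVA is run as 4.1.5 words it, on change scores as the protocol implies, precision is lost in most plausible settings. A chance baseline difference between arms also carries through into the estimate. What is at stake is precision, conditional bias given the observed imbalance, and an undeclared choice between two analyses. Neither model is biased over repeated randomisations, and neither inflates the type I error if it is fixed in advance.

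**Working it through.** **Which tests are affected.** Parameters with one post-baseline value for which a treatment comparison is planned:

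- 5.2.3.8: insulin, HOMA
- 5.2.3.10: apoA1, adiponectin
- 5.2.3.11: fibrinogen, hs-CRP
- 5.2.3.12: NFS, FIB-4, ELF, MACK-3, FIBC3, ABC3D, Pro-C3

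That is 2 + 2 + 2 + 7 = 13. The first six are listed as secondary endpoints in protocol 9.1.

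**Why the MMRM route means adjustment.** With a single post-baseline visit, time has one level, treatment by time is redundant and the unstructured covariance is one residual variance. What remains is absolute change on treatment, diabetic status and baseline.

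**Inputs.** The documents give no SD for these markers and no correlation rho between baseline and week 24, so the values below are assumptions. The number per arm is about 247/3 = 82 (247 randomised, SAP 3.5), assuming an even split and complete data. The plan states no figure on this point, so there is none to reproduce.

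**Variance.** Let k be the week-24 SD divided by the baseline SD, with the baseline SD set to 1.

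- Change score, no baseline term: 1 + k² − 2·rho·k
- Baseline-adjusted: k²(1 − rho²)
- Difference: (1 − rho·k)², which is never negative and is zero when rho·k = 1

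| k | rho | change score | adjusted | ratio | variance reduction |
|---|---|---|---|---|---|
| 1 | 0.3 | 1.40 | 0.91 | 0.65 | 35% |
| 1 | 0.5 | 1.00 | 0.75 | 0.75 | 25% |
| 1 | 0.7 | 0.60 | 0.51 | 0.85 | 15% |
| 1 | 0.9 | 0.20 | 0.19 | 0.95 | 5% |
| 1.5 | 0.3 | 2.35 | 2.0475 | 0.871 | 13% |
| 1.5 | 0.5 | 1.75 | 1.6875 | 0.964 | 3.6% |
| 1.5 | 0.7 | 1.15 | 1.1475 | 0.998 | 0.2% |
| 2 | 0.5 | 3.00 | 3.00 | 1.000 | nil |

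For k = 1 the ratio is (1 + rho)/2. Confidence intervals are narrower by 1 − √ratio: 19%, 13%, 8% and 2.5%.

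**Chance imbalance (k = 1).** One standard error of the baseline difference between two arms is √(2/82) = 0.156 SD. It moves the unadjusted change estimate by (1 − rho) × 0.156, that is 0.109, 0.078, 0.047 and 0.016 SD at rho = 0.3, 0.5, 0.7 and 0.9. The standard error of that estimate is √(4(1 − rho)/82), so the shift is √((1 − rho)/2) = 0.59, 0.50, 0.39 and 0.22 of it.

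**Simulation.**

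- No effect, three arms of 82, a binary stratum in the model, 4,000 trials per setting: variance ratios were 0.66, 0.76, 0.86 and 0.96. Type I error at 5% was 5.3%, 4.9%, 5.1% and 4.5% without baseline, and 5.8%, 4.8%, 4.9% and 4.7% with it (Monte Carlo SE about 0.34 points). Neither fixed model inflates the error.
- Same setting with 20,000 trials, taking the smaller of the two p-values: the error was about 8%, 7%, 7% and 6%. This is the cost of leaving the choice open. It does not suggest that anyone would choose in that way.
- rho = 0.5, true effect 0.4 SD, 75 per arm, alpha 0.025: both models were unbiased, power was 58% without baseline and 72% with it, and the two disagreed on significance in 19% of trials.

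**The case against.** The strongest reply has four parts.

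- **The detailed text prevails over the summary.** SAP 5.2.3.8 names insulin and HOMA and gives them the MMRM, so for those two the detailed text already adjusts. This stands for insulin and HOMA. For the other eleven, adjustment depends on reading a pointer to the glucose section as overriding the ANCOVA named in 5.2.1, and no rule in the SAP says so.
- **The outcome is known.** The protocol speaks of change from baseline, which makes change the natural reading. That is fair, but it supports the unadjusted reading, because the protocol's GLM has only diabetes and dose.
- **Safeguards may exist.** The SAP is to be signed before database lock and appends table mock-ups that we have not seen, and they may fix the model. The SAP is also written against protocol 5.1, while the protocol available is 5.0, so the GLM wording may have changed. Both limits are real. Neither removes a conflict that lies inside the SAP.
- **The consequence is small.** These tests are supportive, multiplicity is not controlled across parameters, and an unadjusted change score is valid. Scores such as NFS, FIBC3 and ABC3D contain age, BMI and diabetes or glucose status, which suggests a high rho; under equal SDs the gain is then near the lower end of the range. This limits the size of the point and is why it is not graded higher.

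**Conclusion.** The concern holds. As written, the SAP supports both a baseline-adjusted and an unadjusted analysis of markers with one post-baseline value, and nothing in its text chooses between them.

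The size depends on assumptions about rho and the SDs. Under equal SDs the loss from omitting baseline runs from substantial at low correlation to slight at 0.9, and under unequal SDs it can vanish. Adjustment never does worse, apart from one degree of freedom. The point should be corrected, but it does not threaten the trial's main conclusion: the CMH analyses of the primary and histological responder endpoints and the sample size are untouched.

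**What to change.** In SAP 4.1.5, define the ANCOVA as a model for absolute change from baseline to week 24, with treatment and diabetic status as factors and the parameter's baseline value as a continuous covariate. State that it is used for every parameter with one post-baseline value, including insulin and HOMA, where it is the same model as the single-visit MMRM.

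Name this model in 5.2.1, in 5.2.3.8 and in the tables of 5.2.3.10 to 5.2.3.12, and replace the when-specified rider with the list of parameters. Record the departure from the GLM wording of protocol 9.7.4 in SAP 4.6.4, or align the protocol if the current version still carries it.

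The cost is one model term, one degree of freedom and a few lines of text. The baseline values are already collected. The change needs to be made before unblinding.
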